3.0 STUDY OBJECTIVES

3.1 Primary Objective

To assess the utility of adding telmisartan at 160 mg/day (or the highest tolerated dose of 40, 80, or 160 mg, daily) to standard GvHD prophylaxis for the prevention of grade II or greater acute graft vs. host disease (aGVHD) in patients receiving allogeneic HCT.

3.2 Secondary Objectives

To assess the safety and tolerability of telmisartan at doses of 160 mg per day (adjusted downward to 80 or 40 mg/day as necessary, on an individual basis for each patient), given orally to patients receiving allogeneic HCT.

3.3 Exploratory Objectives

- 3.3.1 To identify biomarkers that correlate with, or are predictive of, grade III-V GVHD
- 3.3.2 To identify gut and urine flora diversity (Shannon Diversity Index) and changes in the percentages of firmicutes, bacteroidetes, and enterocci, ratio of Clostridia and Lactobacillus species over time, pre- and post- transplantation, in the presence and absence of telmisartan and/or GVHD. The healthy microbiome contains 40-50% firmicutes, 30-40% bacteroidetes, and < 10% enterocci. Some dysbiosis occurs as a result of conditioning and transplantation, with enterocci increasing to ~ 25%. However, during GVHD, these ratios change dramatically, with enterocci increasing to ~50%, and bacteroidetes dramatically dropping.
- 3.3.3 To assess the level of ROCK activity in peripheral blood mononuclear cells, on and off telmisartan treatment, in the presence or absence of GVHD.
- 3.3.4 To measure percentages of lymphocyte subsets, described above, associated with GVHD or suppression of GVHD.

4.0 STUDY POPULATION

The study population will consist of 60 patients undergoing allogeneic HCT for treatment of hematologic malignancies meeting the following criteria. Subject eligibility will be documented by a qualified member of the study team.

4.1 Eligibility Criteria:

4.1.1 Inclusion Criteria

Subjects must meet all of the following inclusion criteria to be eligible for enrollment into the study:

1. Meet the eligibility criteria for HCT as defined by the Standard Operating Procedures (SOP) of the blood and marrow transplantation program of Hackensack University Medical Center.

2. Diagnosis of:

- Acute myeloid or lymphoid leukemia in remission,
- Myelodysplastic syndrome,
- Chronic lymphoid leukemia,
- Non-Hodgkin lymphoma,
- Hodgkin lymphoma,
- Chronic myeloid leukemia in chronic or accelerated phase,
- Myeloproliferative disorder, or
- Multiple myeloma

3. Undergoing allogeneic HSC transplantation from a related or unrelated donor matched at least at 7 of 8 of the HLA-A, -B, -C, and DR loci (“8/8” or “7/8” match)

4. Planned to receive standard GvHD prophylaxis regimen. Subjects receiving rabbit ATG (Thymoglobulin) as part of their conditioning regimen are eligible to participate.

5. Male or female patient age 18 years or older

6. Karnofsky performance status $\geq 70\%$ at time of initiation of pre-transplant conditioning

7. Transplantation-specific co-morbidity score of <5 at time of initiation of pre-transplant conditioning

8. Patients taking antihypertensive medications (including telmisartan) are eligible but the patient must discontinue treatment at least 48 hours prior to first dose of study medication. In cases where the patient’s physicians feel it would be inadvisable to stop all anti-hypertensive treatment prior to starting telmisartan, the patient may continue on amlodipine, hydrochlorothiazide, furosemide, or other non-ARB, non-ACE inhibitors, or non-potassium sparing anti-hypertensives. If ARBs, ACE inhibitors, renin inhibitors, spironolactone, or other potassium sparing drugs cannot be discontinued prior to starting telmisartan, the patient will be ineligible for the study.

9. Capable of giving informed consent and having signed the informed consent form

4.1.2 Exclusion criteria:

Subjects who meet any of the following exclusion criteria will not be eligible for enrollment in this study:

1. Inability to provide informed consent

2. Subjects with known heart failure, advanced renal impairment requiring renal replacement therapy, or liver failure although these patients would most likely not be eligible for HCT, as per SOP of the blood and marrow transplantation program of Hackensack University Medical Center.
3. Subjects taking ACE inhibitors, ARBs, renin inhibitors, potassium supplements, or spironolactone (or any other potassium-sparing diuretics) who cannot discontinue use prior to initiation of study treatment OR who require a high-potassium diet.
4. Patient unable to discontinue current ARB, ACE inhibitor, renin inhibitors, spironolactone, or other potassium sparing hypertension medication for medical or other reasons for two days prior to starting telmisartan
5. Chronic symptomatic hypotension, volume depletion.
6. Planned to receive GvHD prophylaxis regimen with an investigational agent.
7. Pregnant or likely to become pregnant during the period of study, or unwilling to stop nursing.

4.2 Recruitment Procedures

4.2.1 Informed consent process. Patients who are already selected to undergo HCT for a hematologic malignancy (as per eligibility criteria) will be recruited of the John Theurer Cancer Center at Hackensack University Medical Center (Hackensack UMC). Once a potential subject's eligibility has been determined via review of medical records, the subject will be approached for participation by the PI, sub-I, or another qualified member of the research team. The patient will be given a copy of the informed consent form to review. No recruitment materials (e.g., flyers, advertisements) will be used to recruit patients into this study. Patients will not be offered financial or other material incentives to participate in this study.

All patients enrolled in this study must have first met all the eligibility criteria for transplantation in accordance with the treatment plan being used. A conference will be held with the patient and family to discuss this research study. All potential risks associated with participation in this study will be discussed as objectively as possible. From their prior discussions with the transplant team, patients will already have been made aware of the risk of GVHD resulting from allogeneic HCT, as per SOP of the blood and marrow transplantation program of Hackensack University Medical Center.

The issue of how patients on this study may be directly benefited by this treatment protocol, as it is designed to reduce the incidence and severity of GVHD, will be discussed. It will be explained that participation in this study is voluntary. Patients can choose not to participate in this study and still undergo their scheduled allogeneic transplant. All patients who meet the eligibility requirements will be offered the option to participate in this transplant protocol.

4.2.2. Contacting primary physicians. Patients will be asked to provide a list of physicians who prescribe medicine for them or manage their health care. These physicians will be contacted by mail and telephone with information regarding the patient's participation in the telmisartan study and a request that no additional medicines be prescribed by these physicians during the time the patient is receiving telmisartan for the study.

Prior to the study drug being discontinued on day 98, or if the drug is discontinued before day 98, these same primary physicians will be contacted to discuss any anti-hypertensive medications the patient may need as part of their ongoing care.

5.0 STUDY DESIGN

5.1 Overall Study Design

This is multi-center, open-label, prospective study of telmisartan in addition to standard GvHD prophylaxis and treatment for the prevention of acute GVHD in approximately 60 subjects undergoing allogeneic HCT for treatment of a hematologic malignancy. The first 5 patients enrolled will receive telmisartan in an escalating dose according to the following schedule, with day 0 as the day of HCT: day -5 (40 mg), day -4 (80 mg), day -3 (80 mg), day -2 (160 mg), day -1 (160 mg). For these first five enrollees, telmisartan dose will be adjusted for grade 3 or 4 hypotension, as defined by CTCAEv4, as follows: the next day's dose will be one half the previously given dose (e.g. 20 vs. 40, or 40 vs. 80, or 80 vs. 160). If grade 3 or greater hypotension occurs at 20 mg, drug will be discontinued and the patient will be removed from the study. If the patient tolerates 40, or 80 mg, without hypotension, the dose will be increased to 80 or 160 mg, respectively, for the following day. If that (higher) next day's dose is tolerated, 160 mg will be given for the remainder of the trial as outlined below. From day 0 onward, any dose modifications will follow the dose adjustment algorithm outlined in section 5.3.4 below.

If two or more of the first five patients enrolled do not tolerate dose escalation to a stable daily dose of 160 mg by day 0, the trial will be paused, and the remaining volunteers will be enrolled following the same 5-day dose escalation procedure to establish a day 0-100 dose for each subject. All other study safety and endpoints, and dose adjustments will remain as described herein.

If four or more of the first five subjects tolerate 160 mg daily dosing by day 0, the remaining subjects enrolled will begin telmisartan on day -2 at 160 mg/day, as described below.

Subjects will receive 160 mg Micardis brand telmisartan (Boehringer-Ingelheim) in the form of two 80 mg pills, taken together, once daily, starting 2 days prior to HCT (day -2). All subjects will receive telmisartan in addition to the standard GvHD prophylaxis and treatment regimens prescribed by their transplant physician (see section 5.3.5). Systolic and Diastolic Blood pressure will be monitored at least every 4 hours while in the hospital. Patients who develop severe hypotension (\geq grade 3) will have their doses adjusted accordingly (see section 5.3.4 for dose modification schedule). Once the patient is discharged post-HCT, treatment will continue in the outpatient setting. Treatment will continue through Day +98 post-HCT for a total of 104 days (day -5 to day +98) in the first five enrollees, and 101 days (Day -2 to Day +98) in the subsequent subjects, assuming 160 mg is well tolerated in 4 or more of the first 5 subjects. After treatment

discontinuation on or before day +98 post-HCT, subjects will be followed for up to 6 months (Day +180) for primary and secondary endpoints.

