Dispense study drug									X		X		X		X		
Administer study drug		40 mg	80 mg	80 mg	160 mg	160 mg Daily from Day -1 to Day +98											
Provide subject diary									X								
Review treatment compliance										X	X	X	X	X	X	X	
Review Concomitant Medications	X				Continuous												
Record Adverse Events					Continuous												

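### The titration sentence in section 5.1, read literally, gives 160 mg on Day -3 where the 5.1 schedule and Table 3A give 80 mg, and nothing states which text governs

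*Combined protocol and SAP*

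**What the plan says.** Section 5.1 fixes a five-day run-in for the first five patients: "day -5 (40 mg), day -4 (80 mg), day -3 (80 mg), day -2 (160 mg), day -1 (160 mg"). The study-drug row of Table 3A (section 6.0) lists the same 40, 80, 80 and 160 mg and then "160 mg Daily from Day -1 to Day +98". Both hold the dose at 80 mg on Day -4 and Day -3.

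The same paragraph of 5.1 then turns to dose adjustment, in this order:

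- The lead-in: "For these first five enrollees, telmisartan dose will be adjusted for grade 3 or 4 hypotension, as defined by CTCAEv4, as follows".
- The reduction: "the next day's dose will be one half the previously given dose (e.g. 20 vs. 40, or 40 vs. 80, or 80 vs. 160"). Grade 3 or worse hypotension at 20 mg ends treatment and participation.
- The increase: "If the patient tolerates 40, or 80 mg, without hypotension, the dose will be increased to 80 or 160 mg, respectively, for the following day".
- The follow-on: "If that (higher) next day's dose is tolerated, 160 mg will be given for the remainder of the trial as outlined below".

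From Day 0, dose changes pass to the algorithm in section 5.3.4.

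Two rules rest on the run-in. One opens "If two or more of the first five patients enrolled do not tolerate dose escalation to a stable daily dose of 160 mg by day" (day 0 is meant). In that case the trial is paused and the remaining volunteers use the same five-day escalation. Under the other, if at least four of the five tolerate daily 160 mg by Day 0, later subjects start directly at 160 mg on Day -2.

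**The concern.** A patient who tolerates 80 mg on Day -4 without hypotension is due 80 mg on Day -3 by the schedule and Table 3A, and 160 mg by the titration sentence. Both cannot be followed. The follow-on sentence points the same way as the titration sentence: once 40 mg and then the higher 80 mg have been tolerated, 160 mg is to be given from then on. No text limits these two sentences to patients whose dose was halved, and none says which text takes precedence.

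The run-in is short and serves as a decision step. Its outcome in five patients sets the starting procedure for the rest of the planned 60. If it fails, the same escalation, with the same ambiguity, applies to the remaining 55 (60 - 5, ignoring replacements).

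**Working it through.** **Inputs.** The schedule, the halving rule, the titration sentence, the follow-on sentence and the four-of-five rule all come from section 5.1. The tabulated doses come from Table 3A.

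**The plan's own figure.** Section 5.1 gives treatment "for a total of 104 days (day -5 to day +98) in the first five enrollees". Check: 98 - (-5) + 1 = 104. For later subjects, 98 - (-2) + 1 = 101, also as stated. Both hold under either reading.

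**Event-free patient.**

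| Reading | Day -5 | Day -4 | Day -3 | Day -2 | Day -1 | Total | 160 mg doses |
|---|---|---|---|---|---|---|---|
| Schedule and Table 3A | 40 | 80 | 80 | 160 | 160 | 520 mg | 2 |
| Titration sentence, literal | 40 | 80 | 160 | 160 | 160 | 600 mg | 3 |

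Sums: 40 + 80 + 80 + 160 + 160 = 520 and 40 + 80 + 160 + 160 + 160 = 600. Four of the five days agree. The whole difference is 160 - 80 = 80 mg on Day -3.

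**Can the scheduled Day -3 dose arise under the literal rule?** Treat each of the five days as either tolerated without hypotension (next dose doubled, up to 160 mg) or grade 3-4 hypotension (next dose halved). That gives 2^5 = 32 patterns. After 80 mg on Day -4, the Day -3 dose is 160 mg if tolerated and 40 mg if not. So none of the 32 patterns has 80 mg on both days. Grade 1 or 2 hypotension is outside this two-way split, because neither sentence covers it.

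**Patient with grade 3-4 hypotension at the first 160 mg dose who tolerates everything else.**

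| Reading | Day -5 | Day -4 | Day -3 | Day -2 | Day -1 |
|---|---|---|---|---|---|
| Schedule, with the rule used only to re-escalate | 40 | 80 | 80 | 160 (event) | 80 |
| Titration sentence, literal | 40 | 80 | 160 (event) | 80 | 160 |

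Under the literal reading this patient is back on 160 mg on Day -1. Under the schedule the patient is on 80 mg on Day -1. Because 5.3.4 governs from Day 0 and asks for a week at a reduced dose before an increase, 160 mg would then not be re-established by Day 0.

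**Effect on the decision.** With five patients, 0 or 1 failures lets later subjects start at 160 mg, and 2 to 5 failures pauses the trial. The rule covers every count without overlap. If exactly one other patient has failed, classifying this patient one way or the other moves the count from 1 to 2, and so from proceeding to pausing.

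**Events at lower doses.** Where hypotension first occurs at 80 mg on Day -4, both readings give 40, 80, 40, 80, 160. Where it occurs at 40 mg on Day -5, both give 40, 20, 40, 80, 160, provided a step from 20 to 40 mg is assumed, since 5.1 does not state one.

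**The case against.** The strongest reply is that context supplies the missing limit. The titration sentence sits in a block introduced as adjustment for grade 3 or 4 hypotension. The block runs: reduce, stop at the lowest dose, raise again. Section 5.3.4 follows a similar order for later dosing. Read as re-escalation after a reduction, the sentence does not touch an event-free patient and the conflict disappears. The literal reading also makes the second 80 mg day unreachable in the two-way enumeration, although it is written in both 5.1 and Table 3A. That suggests loose wording more than a rival scheme.

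This makes the re-escalation reading plausible but does not settle it. Section 5.3.4 expressly ties its re-escalation to a previous dose reduction; 5.1 does not. The halving rule can produce 20, 40 or 80 mg, yet the upward rule starts at 40 mg, so a patient reduced to 20 mg has no stated way up. The steps it does give, 40 to 80 and 80 to 160, are the schedule's own steps.

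Three stronger readings are tempting, and the documents do not support them:

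- A reader might infer that the first five patients have no single escalation scheme. The schedule is written the same way twice, and for an event-free patient the readings differ on one day of five.
- A reader might infer that the four-of-five rule is never one fixed test. An event-free patient is on 160 mg on Day -2 and Day -1 either way. The result can change only for a patient with hypotension on the way up.
- A reader might take a simple carry-over calculation as the size of the problem. With half the drug retained per day, the amount after the Day -3 dose is 210 versus 130 mg-equivalents, 62% more. That is the largest single-day gap. It falls to 265 versus 225 (18%) on Day -2 and 292.5 versus 272.5 (7%) on Day -1. The calculation assumes linear kinetics, while section 1.3.5 describes them as nonlinear. Section 2.1 also reports no apparent further fall in blood pressure at doses up to 160 mg in hypertension trials, so a doubled dose cannot be read as a doubled hypotension risk.

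**Conclusion.** The inconsistency is real and narrow. As worded, the schedule and Table 3A on one side and the titration sentences on the other give different Day -3 doses for a patient who tolerated 80 mg on Day -4. For an event-free patient the size is 80 versus 160 mg on that day, two versus three 160 mg doses before Day 0, and 520 versus 600 mg in total.

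It is more than missing detail, because one kind of patient can be classified differently: one with grade 3-4 hypotension at the first 160 mg dose who then tolerates 160 mg on re-challenge. This assumes that a single tolerated 160 mg dose on Day -1 could count as a stable dose by Day 0, which 5.1 does not define, and that the 5.3.4 algorithm applies to any increase on Day 0. It changes the starting procedure for later subjects only when exactly one other patient in the five has failed.

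Sample size, power, significance level and the 104-day and 101-day treatment totals are unaffected. The point is an internal inconsistency, not a criticism of the chosen design, and it takes no position on which dose is right.

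**What to change.** Reconcile the day-by-day schedule in 5.1, the two titration sentences that follow it, and the study-drug row of Table 3A. State in 5.1:

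- whether the increase on the following day applies only after a hypotension-driven reduction or to every patient in the run-in;
- which text governs the Day -3 dose;
- what follows a tolerated 20 mg dose, since the present rule is silent.

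The choice of scheme is for the sponsor's clinicians. The cost is a short clarification in 5.1 and a check of Table 3A, with no added patients, visits or procedures.

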5.2 Study Endpoints

5.2.1 Efficacy Endpoints

- Grade II GVHD as per 1994 Consensus Conference on Acute GVHD Grading criteria [104]
- Grade III-IV GVHD as per 1994 Consensus Conference on Acute GVHD Grading

5.2.2 Safety Endpoints

- Grade III-IV hypotension as per the National Cancer Institute's Common Terminology Criteria for Adverse Events version 4.0 (CTCAE)
- Relapse/progression of disease
- Primary graft delay, defined as ANC < 500 x 3 consecutive draws at 28 days, and < 5% donor CD3 T cell chimerism at day 28 and/or day 56.
- Primary graft failure, defined as ANC < 500 at 56 days x 3 consecutive draws and < 5% donor CD3 T cell chimerism as determined by standard of care.
- Secondary graft failure (loss of engraftment), defined as loss of ANC > 500 after 3 days of ANC > 500, or loss of chimerism subsequent to detection of chimerism
- Non-relapse mortality: Occurrence of unexpected, study drug-related

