7.2.3 Engraftment

Appearance and rise in peripheral blood neutrophils will be monitored on a daily basis for the first 2 weeks, and then twice weekly. Absolute neutrophil counts that never reach 500 in the first 28 days and/or platelet counts that drop below 20,000 and remain below that number during the 28 day period will be considered “late engraftment” until repeat evaluation at days 56 and 84 and scored as a primary failure to engraft if no engraftment occurs by those time points. Chimerism analysis of peripheral blood CD3+ cells is routinely assessed at 28, 56, and 84 days after transplantation, and will also be used in the definition of engraftment (5% donor CD3 cells), as described above (see 5.2.2). These data will be collected for retrospective analysis.

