Monitoring Look	Number of Patients at Monitoring Look	Stop if Number of Toxicities is at least
1	9	2
2	21	3
3	33	4
4	45	5
5	58	6
6	60	7

The trial will be terminated if 2 or more patients out of the first 9 patients receiving experimental drug, Telmisartan, experience graft failure by day 100. If out of the first 21 patients, 3 or more have graft failure by day 100 then trial will be stopped. The boundaries were obtained such the Type I error, fixed at 1%, was spent over the multiple looks, hence the probability of stopping the trial prematurely by chance is 0.01.

Table 10. Operating characteristics for the stopping boundaries for Graft Failure Day 100

Probability Of Toxicity	Probability of crossing low bndry	Probability of stopping low bndry	Expected sample size low bndry	Probability of crossing high bndry	Probability of stopping high bndry	Expected sample size high bndry
0.07	0.373	0.373	46.1	0.365	0.365	46.2
0.08	0.477	0.477	42.4	0.467	0.466	42.5
0.09	0.576	0.576	38.7	0.565	0.565	38.8
0.10	0.666	0.666	35.0	0.655	0.654	35.1
0.11	0.744	0.744	31.6	0.734	0.733	31.7
0.12	0.809	0.809	28.5	0.799	0.798	28.6

Bndry, boundary.

From the operating characteristics, the probability of stopping the trial due to graft failure if the level of toxicity is at high level of 12% is 0.798. The expected sample size at termination of the trial is 28.6, if Telmisartan in fact more toxic than standard treatment.

Telmisartan Intolerance (includes angioedema and grade 3 or greater drug related adverse events after dose adjustments)

We use 5% as our acceptable rate of intolerance for drug treatment. Using repeated significance testing (Jennison and Turnbull) with 5.0% as lower proportion and 11.0% as higher proportion, 1% alpha level, and 80% power to for early termination, shape parameter of the boundary, delta=0.2, giving priority to the alternative hypothesis and continuous monitoring, the following stopping guidelines were computed by the *toxbdry* function in the Clinfun package in R 3.2.0.

Table 11. Stopping Boundaries for Intolerance to Telmisartan at Day 100

Monitoring Look	Number of Patients at Monitoring Look	Stop if Number of Toxicities is at least
1	8	2
2	22	3
3	38	4
4	55	5
5	60	6

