10.2 Risk/Benefits

Patients undergoing allogeneic hematopoietic stem cell transplantation using myeloablative regimens and cells from related or unrelated donors face considerable risks associated with this treatment. These risks include prolonged periods of marrow hypoplasia requiring blood component and antibiotic support. Even after engraftment, the immunological dysfunction persisting for months after transplantation can lead to opportunistic infections. A small proportion of patients will fail to achieve sustained donor cell engraftment, requiring re-conditioning and a second transplant. The primary causes of treatment failure, however, arise from acute and/or chronic GvHD and from relapse of disease.

In phase III and post-marketing safety studies, telmisartan, 80 or 160 mg per day, was found to have a very good safety profile, with the incidence of reported “poor tolerability” of only 0.5% [106]. In theory, due to its anti-inflammatory actions, telmisartan could increase the risks of primary or secondary graft failure, delayed engraftment, or early post-transplant relapse of disease. However, immunosuppression or increased risk of infection were not drug related adverse events, either in controlled Phase III trials or in post-marketing review.

Other serious complications of allogeneic HSC transplantation could occur through unforeseen interactions with other medications or as a result of chemotherapy administration. It is unlikely, but theoretically possible, that successful reduction of acute IT GvHD could redirect allo-reactive T cells to the skin or lungs to produce higher levels of GVHD at those sites. In addition to telmisartan, subjects will be receiving standard GvHD prophylaxis as ordered by their transplant physician.

The Transplantation Program team of physicians, advanced-practice nurses, nursing staff, pharmacists, social workers, nutritionists, and physical therapists manages patients undergoing allogeneic HSC transplantation at HackensackUMC. Patients undergo medical care in dedicated inpatient and outpatient units. The resources of the Transplantation Program ameliorate the potential risks of allogeneic HCT in the treatment of malignant diseases. These same resources will apply to patients enrolled into this clinical study. In addition, a research nurse coordinator will monitor patients while receiving telmisartan. All adverse events will be recorded and scored per CTCAEv4.

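### A patient with recovered neutrophils and donor CD3 below 5% at every test meets none of the three graft-failure definitions in 5.2.2 and adds no event to the Table 9 stopping rule

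*Combined protocol and SAP*

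**What the plan says.** Section 5.2.2 of the combined protocol and SAP defines three graft events.

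- Delay: "Primary graft delay, defined as ANC < 500 x 3 consecutive draws at 28 days, and < 5% donor CD3 T cell chimerism", with the chimerism result taken at Day 28 and/or Day 56.
- Primary failure: "Primary graft failure, defined as ANC < 500 at 56 days x 3 consecutive draws and < 5% donor CD3 T cell chimerism".
- Secondary failure: loss of an ANC above 500 after three days above it, "or loss of chimerism subsequent to detection of chimerism".

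The first two join their conditions with *and*. The third joins them with *or*.

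Section 7.2.3 starts late engraftment from blood counts only: "Absolute neutrophil counts that never reach 500 in the first 28 days and/or platelet counts that drop below 20,000". It then says that CD3 chimerism "will also be used in the definition of engraftment (5% donor CD3 cells), as described above (see 5.2.2"). It places the CD3 tests at Days 28, 56 and 84.

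Section 8.4 monitors graft failure at Day 100, described as including delayed engraftment and failure. It gives no definition of its own and does not say whether secondary failure counts. The reference rates are 7% (expected, from the center registry) and 12% (unacceptable). The text under Table 10 states that "the probability of stopping the trial due to graft failure if the level of toxicity is at high level of 12% is 0.798".

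**The concern.** A graft can fail in two ways that look different in the blood. Either counts stay low, or the patient's own marrow recovers and counts rise without donor cells. The *and* in 5.2.2 captures the first. It captures the second only through the secondary-failure limb, and that limb needs donor chimerism to have been seen first.

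Section 10.2 describes the hazard in terms of donor cells ("A small proportion of patients will fail to achieve sustained donor cell engraftment") and names primary or secondary graft failure as a theoretical risk of telmisartan's anti-inflammatory action. Graft failure is also one of five criteria that can stop the trial. If one form of it is not a defined event, the rule may have less chance of detecting an unacceptable rate than Table 10 shows.

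**Working it through.** **1. Three illustrative records against 5.2.2**

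| Record | Delay | Primary failure | Secondary failure |
|---|---|---|---|
| A: ANC 200, donor CD3 0% at Days 28 and 56 | met | met | – |
| B: ANC 1,800 throughout; donor CD3 60% at Day 28, 0% at Day 56 | not met (ANC) | not met (ANC) | met (chimerism detected, then lost) |
| C: ANC 1,800, donor CD3 0% at Days 28 and 56 | not met (ANC) | not met (ANC) | not met (ANC not lost; chimerism never detected) |

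The count-based trigger in 7.2.3 does not catch C on its ANC, and catches it on platelets only if they are also low. B and C have the same Day 56 result, and only B is a defined event. Because the first scheduled CD3 test is at Day 28, donor cells present only before then would not be recorded.

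**2. Reproducing the plan's figures**

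Inputs: Table 9 (stop at 2 of 9, 3 of 21, 4 of 33, 5 of 45, 6 of 58, 7 of 60), continuous monitoring, 60 patients. Let b(n) be the limit that applies at patient n: 2 for n up to 9, 3 up to 21, 4 up to 33, 5 up to 45, 6 up to 58, 7 up to 60. With p the probability of a *counted* event, and P_n(k) the probability of being unstopped with k events after n patients,

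P_n(k) = P_{n−1}(k)·(1−p) + P_{n−1}(k−1)·p for k < b(n).

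Any mass reaching b(n) is a stop.

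| p | Crossing, computed | Table 10 (high boundary) | Expected N, computed | Table 10 |
|---|---|---|---|---|
| 0.07 | 0.3652 | 0.365 | 46.2 | 46.2 |
| 0.12 | 0.7994 | 0.799 | 28.6 | 28.6 |

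Leaving out a crossing at the last patient gives 0.7985 at 12%, against the stated 0.798. The figures reproduce. (That 0.365 at the acceptable rate does not match the 1% error stated in 8.4 is a separate matter.)

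**3. If the 7% and 12% rates include records like C and the trial does not count them**

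Let f be the share of true failures that look like record C. The documents give no value, so f is assumed. Counted rate = 0.12 × (1 − f).

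| f | Counted rate | Chance of stopping at a true 12% | Expected N |
|---|---|---|---|
| 0 | 0.120 | 0.799 | 28.6 |
| 10% | 0.108 | 0.719 | 32.4 |
| 20% | 0.096 | 0.620 | 36.6 |
| 30% | 0.084 | 0.507 | 41.0 |
| 40% | 0.072 | 0.386 | 45.5 |

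The same under-count applies to an acceptable drug. At f = 40% its counted rate is 0.07 × 0.6 = 0.042, and the chance of stopping is 0.118.

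**4. If the registry 7% was counted on the narrow wording**

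Nothing is lost on that scale, and 0.80 at 12% stands. But if the event is then widened and Table 9 left alone, the acceptable rate becomes 0.07 / (1 − f).

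| f | Acceptable rate on the wider definition | Chance of stopping |
|---|---|---|
| 10% | 0.078 | 0.44 |
| 20% | 0.0875 | 0.54 |
| 30% | 0.100 | 0.66 (Table 10: 0.655) |

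These compare with 0.365 at 7%.

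**The case against.** - **Not every rejection is missed.** A reader might infer that any patient whose own marrow recovers after rejection escapes the rule. The documents do not support that. Record B is secondary failure under 5.2.2 with no ANC condition, although 8.4 leaves open whether secondary failure enters Table 9. The gap is confined to chimerism never detected, and 5.2.2 sets no threshold for detection.
- **The plan does not say that record C is engrafted.** A reader might infer this, but 7.2.3 puts 5% donor CD3 into the definition of engraftment. Record C is unclassified. The practical result is still that no defined event reaches Table 9.
- **CD3 is a T-cell measure.** It does not show whether the neutrophils are of host or donor origin. Marrow CD34 chimerism is recorded only after Day 75, and only if a standard-of-care specimen exists. Rabbit ATG conditioning is allowed. Requiring both conditions could be a deliberate guard against false positives, though the plan does not say so. This carries weight for scoring delay on CD3 alone at Day 28. It carries less at Day 56, because the secondary-failure limb already accepts chimerism alone.
- **The loss of power is conditional.** It arises only if the 7% and 12% rates include such patients, and 8.4 does not state how the registry events were defined. This stands in full.
- **The rule does not stop discriminating.** A reader might set 0.386 (12%, under-counted by 40%) beside 0.365 (7%, fully counted) and conclude that it does. That is not like for like. Under the same under-count the contrast is 0.386 against 0.118.
- **These patients remain visible.** CD3 results are collected and the DSMB meets monthly. That is a real safeguard, but it does not feed the numerical boundary.

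**Conclusion.** The definitional gap is real and follows from the text alone. Primary non-engraftment with ANC above 500 and donor chimerism never detected falls outside all three definitions in 5.2.2. This conflicts with the use of 5% donor CD3 in 7.2.3, and with 5.2.2's own treatment of the same end state when chimerism was once present.

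The numerical effect is not established. It rests on two things that the documents do not give: the share of failures of this kind, and the definition behind the 7% and 12% rates. The losses in step 3 apply only if those rates include such patients. The assumed shares have no anchor in the plan and serve only to show sensitivity. The point is worth correcting because it concerns a safety endpoint that feeds a stopping rule and the tests needed are already scheduled.

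**What to change.** 1. In 5.2.2, count donor CD3 below 5% at Day 56, with chimerism never detected, as primary graft failure whatever the ANC. State what level counts as detection.
2. Use one definition in 5.2.2, 7.2.3 and 8.4, and say whether secondary failure counts toward Table 9.
3. Settle the Day 28 delay criterion in that reconciliation. Scoring delay on CD3 alone is debatable and is not proposed here.
4. Apply the agreed definition to the registry. If the 7% reference changes, reconsider the 12% limit on the same scale and recompute the Table 9 boundary and Table 10. Widening the event without this step could raise the chance of stopping for an acceptable drug, as step 4 of the working shows.

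Cost: a few sentences, a registry re-count and possibly a new boundary. No new test is needed, since sections 6.3 and 7.2.3 already schedule CD3 chimerism at Days 28 and 56. The event count may be somewhat higher.
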